1.3 Preliminary Data

Over the last 2.5 years our group has conducted a series of studies on the use of wireless technology in preterm and term neonates under the SMART Hospital Project. We started the project by conducting a systematic review of all published literature on wearable devices in neonates²⁹ and children, followed by a Scoping Review on the use of wireless technology in hospitalized children.³⁰ After these reviews, we selected a wireless sensor developed by the Laboratory of [name] at Northwestern University optimized & commercialized by Sibel Health, Inc. for evaluation. The safety and accuracy of these sensors were previously investigated in a few neonates for short periods of time, however we felt that healthcare technology assessment in a variety of NICU infants for longer recording periods was necessary.^{23,24} To this end, we established a Research & Development collaboration with Sibel Health, Inc. and conducted a *phase 1a* study in our NICU at the Montreal Children's Hospital to evaluate ANNE One® sensors. A hardware/software system called BioDASH was developed for this study by Ikenesia Inc. (<https://www.ikenesia.com/>; Montreal, Quebec, Canada) to allow simultaneous recording of vital signs from a wired (standard of care) and a wireless system in 25 infants, 8h per day during 4 consecutive days.³¹ In order to ensure the research team performing was adequately prepared to perform the Phase 1a study, they participated in training on how to handle, place and remove the wireless sensors prior to the start of data collection. There were no reports or feedback by the research team of any difficulty related placement or removal of the wireless skin sensors. Heart rate, respiratory rate, oxygen saturation, and skin temperature were recorded. Full analysis of the data is underway, with some results presented and published. HR analysis of the first 10 patients enrolled was presented at the Pediatric Academic Society (PAS) meeting in Washington, DC USA (April 27-May 1 2023) showing an excellent agreement between the two systems for HR values.³² (**Figure 2**).

[figure not shown]

Figure 2. Regression analysis of ANNE One® and Philips HR signals for HR.

This accuracy analysis was recently completed for all 25 infants and confirmed the strong agreement between HR recorded by the wired and wireless systems with ANNE® One, showing a strong potential for wireless monitoring in the NICU³³ (**Figure 3**).

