2.2 Aims

Healthcare technology assessment is the multidisciplinary evaluation of medical technologies with regard to **feasibility, safety, efficacy**, indications for use, cost, and cost-effectiveness. A complete assessment should explore the scientific, ethical, economic, and social reasons for adopting a technology and it may influence the quality of service and distribution of resources.

In this multicenter study, we aim to assess the first 3 important criteria.

Aim 1 – To determine the **feasibility** of using a wireless system immediately after delivery and for the first 2h of age, while in the obstetrical center under unsupervised parents' care. The following outcomes will be measured for both wired and wireless systems:

- a. Percentage of time for which HR, RR, SpO₂ and T_{skin} data are displayed.
- b. Occurrence of gaps in signal detection/recordings (% and length).
- c. Causes of the gaps in signal detection/recordings.
- d. Descriptive analysis of user surveys and their satisfaction with the wireless system.

Aim 2 - To investigate the **safety** of using this wireless system immediately after delivery and for the first 2h of age. The following outcomes will be measured for both wired and wireless systems:

- a. Skin score to be determined by a blinded dermatologist using de-identified pictures of the skin after removal of the sensors of each system.
- b. Pain scale to assess any discomfort or pain during the removal of the sensors.
- c. Clinically significant events detected by the wired system (HR < 100 bpm or SpO₂ < 80%) but missed by the wireless system.

Aim 3 – To assess the **accuracy** of this wireless system in measuring HR, RR, SpO₂ and T_{skin} signals compared with the “standard of care” wired system. The following outcomes will be computed:

- a. Correlation coefficient
- b. Slope
- c. Variance accounted for
- d. Bias

Further subgroup analyses will be conducted to assess for systematic differences in feasibility, safety, and accuracy of the wireless system between the following:

- High vs. Low and Middle income countries
- Female vs. Male subjects
- Term vs. Preterm (born < 37 weeks gestational age) infants
- C-section vs. Vaginal delivery

- Skin pigmentation

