3.3.3 Study Interventions

Each newborn enrolled in the Study will be monitored simultaneously by both the standard of care (control) wired vital sign monitoring system (Infinity M540 monitor, Draeger, Germany) and the wireless monitoring system (intervention) (ANNE Arc chest sensor, SIBEL Health, Illinois, USA and Limb sensor (RAD7, Masimo) (Figure 9).

Both monitoring systems, will simultaneous record heart rate, respiratory rate, oxygen saturation, and skin temperature for the first 2h of age.

Figure 9. Monitoring systems – ECG and temperature

Figure 10. Monitoring Systems – SpO2

All materials and equipment required for the conduct of the study will be provided to the participating sites by the lead site. All research team members at all sites will be trained on the placement and removal of the wireless and wired monitoring including appropriate cleaning and disinfecting protocols. Training on the use of the BioDash system will also be provided as part of the study training at all sites.

Vital Sign Monitoring:

If a baby is born via:

1. *Vaginal Delivery:* Following normal, vaginal delivery, the wireless skin sensor monitoring system (Anne Arc & RAD7 Limb,Sibel Health Inc - Masimo) will be immediately placed on the newborn. In order to promote the standard practice of bonding between newborn and mother the standard of care wired monitoring system (Infinity Monitor, Drager) will be placed on the newborn after 10-20 min of age.
2. *C-section:* Immediately before birth, the infant will be randomized for the type of monitoring system to be applied first: a) the wireless sensors (Anne Arc & RAD7 Limb,Sibel Health Inc - Masimo) or b) standard of care wired system (Infinity Monitor, Drager). In order to promote the standard practice of bonding between newborn and mother the second monitoring system will be placed on the newborn after 10-20 min of age.

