As part of the Smart Hospital Project, this Study and potential future research studies to improve the quality, accuracy and efficiency of monitoring neonates admitted in the NICU, the participants' information may be shared with academic or commercial third parties and used by the research team in other related research studies. Any use of the RI-MUHC and participating site's data in future research studies will be approved by competent research ethics boards and no data that could identify the participant will be shared. Participants at all participating sites will be asked to consent to the sharing of their data collected during this study as well as for use in future research in the field of neonatal care and monitoring. The participants' data will be kept confidential to the extent required by applicable laws. The research agreements with the participating sites will include all the terms and conditions required for the use and sharing of the data from participating sites.

4 Statistical Analysis and Rationale

Sample size: The proposed sample size is 100 newborns/site (n=600) to be recruited over 2 years from start of the Study at each site.

The expected mean and standard deviation are required for estimating the mean effects which is used to determine the absolute precision. In our first study with wireless sensors (see preliminary data) or *phase 1a*, 100 patient recordings (25 infants x 4 days) were expected but only 96 were obtained, resulting in a 4% drop-out rate. Further, the average coverage across wired HR signals was $98.7 \pm 2.2\%$, while that of wireless signals was $85.3 \pm 14.3\%$. Assuming a two-sided significance of 0.05, a study power of 0.9, and accounting for the drop-out rate of 0.04 in all calculations, we can expect an effect size of 2.7% in HR coverage, with the selected sample size of 600 infants. In the case of SpO₂ monitoring, the average coverage was $93.9 \pm 6.3\%$ in the wired system and $66.5 \pm 20.8\%$ in the wireless. In our proposed study, we

can thus expect a difference of 3.46% in SpO₂ coverage. For the statistical measures used to assess the agreement between the wired and wireless vital signals, the average findings from *phase 1a* are reported in the Table. Using the same parameters listed previously, the margin of error expected for each statistical measure in the proposed study can be found.

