Statistical measure		Correlation coefficient, C	Proportionality constant, k	Variance accounted for (VAF)	Mean difference (bias), d
Average result in phase 1a	Heart rate (HR)	0.96 ± 0.03	1.00 ± 0.00	91.5 ± 6.5%	0.04 ± 0.32 bpm
	Oxygen saturation (SpO ₂)	0.53 ± 0.23	1.01 ± 0.01	18.9 ± 20.8%	1.43 ± 1.4%
Expected margin of error	Heart rate (HR)	0.01	0.00	1.24%	0.06 bpm
	Oxygen saturation (SpO ₂)	0.04	0.00	3.97%	0.26%

Statistical analytical approach: Descriptive analyses will first be applied to the demographic data. Accuracy analysis of the wireless system to capture the vital signs will be done by using a statistical measure of the strength of a linear relationship between the two systems (correlation coefficient), a measurement of the steepness of this correlation (slope), the ratio of explained and target variance (variance accounted for), and a Bland-Altman plot analysis to evaluate *bias* between the mean differences and estimate an agreement interval.

Each participating site has the facilities and capacity to provide the estimated number of infants to establish feasibility, safety, and accuracy of the device. The wireless device sensors and system being used in the study is approved by Health Canada for research on neonates. Each site will obtain approval from their local and country specific health authorities, as required.

5 Ethical, Legal and Regulatory Considerations

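### Section 4's 3.46% for SpO2 coverage does not follow from its own SD, the HR coverage figure fits an unpaired formula, and the margin-of-error row is a 90%-power detectable difference

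*Combined protocol and SAP*

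**What the plan says.** The sample-size paragraph of section 4 sets 100 newborns at each of six sites (600 in all) and fixes common inputs: "Assuming a two-sided significance of 0.05, a study power of 0.9, and accounting for the drop-out rate of 0.04 in all calculations".

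For heart rate it takes phase 1a coverage of 98.7 ± 2.2% (wired) and 85.3 ± 14.3% (wireless) and concludes: "we can expect an effect size of 2.7% in HR coverage, with the selected sample size of 600 infants". For SpO2 it takes 93.9 ± 6.3% (wired) and 66.5 ± 20.8% (wireless) and states that the investigators "can thus expect a difference of 3.46" percent.

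It then turns to the agreement measures: "Using the same parameters listed previously, the margin of error expected for each statistical measure" is to be read from the table. The table row "Expected margin of error" gives 1.24% for HR VAF, 3.97% for SpO2 VAF, 0.06 bpm for HR bias and 0.26% for SpO2 bias. The phase 1a SD of SpO2 VAF is 20.8%.

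On design, section 3.3.3 says: "Each newborn enrolled in the Study will be monitored simultaneously by both the standard of care (control) wired vital sign monitoring system", together with the wireless system. Section 2.2 says of the feasibility outcomes, which include coverage: "The following outcomes will be measured for both wired and wireless systems". Phase 1a was also built "to allow simultaneous recording of vital signs from a wired (standard of care) and a wireless system in 25 infants" (section 1.3).

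**The concern.** Two quantities with the same SD, the same number of infants and the same error rates should have the same detectable difference. Section 4 gives 3.46% for one and 3.97% for the other. Two further things look wrong once the arithmetic is traced. The HR coverage figure appears to treat wired and wireless as separate groups of infants. The row presented as precision appears to contain a power term, which a confidence-interval margin does not have.

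These are the only figures in the plan that say what 600 infants can detect or estimate. A reader who relies on them would have one that contradicts its inputs, one whose apparent model is not the study's design, and a row that does not mean what its label says.

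**Working it through.** **Inputs (section 4).** Two-sided 0.05 and power 0.90 give z = 1.9600 + 1.2816 = 3.2415. Evaluable infants: 600 x 0.96 = 576. SDs are those quoted from phase 1a.

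**Step 1: find the formula behind the stated figures.** The plan names none, so it is inferred. Two independent groups of 576, with the wireless SD used for both, give

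difference = 3.2415 x SD x sqrt(2/576) = 0.191 x SD.

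| Quantity | SD | 0.191 x SD | Stated |
|---|---|---|---|
| HR coverage | 14.3 | 2.73 | 2.7 |
| HR VAF | 6.5 | 1.24 | 1.24 |
| SpO2 VAF | 20.8 | 3.97 | 3.97 |
| HR bias (bpm) | 0.32 | 0.061 | 0.06 |
| SpO2 bias | 1.4 | 0.267 (0.258 to 0.277 for SD 1.35 to 1.45) | 0.26 |
| HR correlation | 0.03 | 0.006 | 0.01 |
| SpO2 correlation | 0.23 | 0.044 | 0.04 |
| **SpO2 coverage** | **20.8** | **3.97** | **3.46** |

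The VAF cells identify 576: with 600 per group they would be 1.22 and 3.89. Since sqrt(2/576) = 1/sqrt(288), the same numbers could also be a one-sample calculation on 288 infants. The power term is present either way.

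**Step 2: can 3.46 be rescued?**
- Rounding of 20.8 allows only 3.96 to 3.98.
- Required SD: 3.46 / 0.191 = 18.1.
- Power at 3.46 with SD 20.8: Phi(3.46 / (20.8 x sqrt(2/576)) - 1.96) = Phi(0.863) = 0.81.
- Infants needed at 90% power: 2 x (3.2415 x 20.8 / 3.46)² = 760 evaluable per group.
- HR coverage of 2.7 is also consistent with 600 per group (2.68), or with both SDs at 300 per group (2.71), though both omit the drop-out. The SpO2 figures would then be 3.89 and 4.07.
- Without fixing the multiplier: if both coverage figures scale with the wireless SD, their ratio should be 20.8/14.3 = 1.45. The stated ratio is 1.26 to 1.31 after allowing for rounding.

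**Step 3: the paired calculation.** With both systems on each infant, the relevant SD is that of the within-infant difference, sqrt(a² + b² - 2 x rho x a x b), and the detectable difference is 3.2415 x SD / sqrt(576) = 0.135 x SD. The documents give no rho, so the whole range is shown, ignoring site.

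| | SD of difference, rho = +1 / 0 / -1 | Detectable difference |
|---|---|---|
| HR coverage | 12.1 / 14.5 / 16.5 | 1.63 / 1.95 / 2.23 |
| SpO2 coverage | 14.5 / 21.7 / 27.1 | 1.96 / 2.94 / 3.66 |

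On the stated inputs, a paired HR figure cannot exceed 2.23, so 2.7 is not a paired result. If an intraclass correlation (ICC) of 0.01 by site is assumed (the documents give none), the factor is sqrt(1 + 95 x 0.01) = 1.40 with 96 infants per site. The ranges become 2.28 to 3.11 for HR (2.73 at rho = 0) and about 2.7 to 5.1 for SpO2 (4.10 at rho = 0).

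**Step 4: the margin row.** Each measure is one value per infant, so a simple 95% half-width is 1.96 x SD / sqrt(576) = 0.0817 x SD. The stated row is larger by 3.2415 x sqrt(2) / 1.96 = 2.34.

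| | Stated | 95% half-width | With assumed ICC 0.01 |
|---|---|---|---|
| HR VAF | 1.24% | 0.53% | 0.74% |
| SpO2 VAF | 3.97% | 1.70% | 2.37% |
| HR bias | 0.06 bpm | 0.026 bpm | 0.036 bpm |
| SpO2 bias | 0.26% | 0.11% | 0.16% |

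**The case against.** The strongest reply is that the formula is inferred. The 2.7% has two significant figures and fits several configurations. A paired calculation at zero correlation with a site ICC of 0.01 also gives 2.73. A correlation of 0.8 with an ICC of 0.016 would give about 2.70 for HR and 3.47 for SpO2, close to both stated figures. This stands to the extent that 2.7 is not shown to be too large or too small for the real design. It does not rescue the text, because the plan states neither a correlation nor an ICC. Nor does it explain why the same SD under the same parameters yields 3.97 in the table.

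On the margin row, one can say that the stated parameters include the power, so the power term is disclosed, and that the row errs towards caution. Both are true. The label still tells readers that they are looking at interval precision, and they are not.

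The remedy has limits as well. Phase 1a used an earlier chest sensor in NICU infants for 8 hours a day over 4 days, whereas this study uses a redesigned chest sensor and a different limb sensor for 2 hours after birth. The plan does not say whether its SDs are per infant or per recording. An SD of differences from phase 1a is therefore provisional.

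Finally, the practical consequence is small: the sample size is set at 100 per site, and no decision threshold uses 3.46. That argues for a light correction, but it does not make the figures right.

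**Conclusion.** The concern holds in all three parts.

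1. The SpO2 coverage figure conflicts with its own inputs. It should be 3.97% if the SD of 20.8 is right; if 3.46% is right, the SD is about 18.1. The documents do not show which. The 3.97% rests on an inferred formula, but the contradiction with the SpO2 VAF cell needs only the plan's statement that the parameters are the same.
2. The HR coverage figure is reproducible, but only as an unpaired comparison if the plan's stated inputs are used. The fault is the model. The direction of any error is not established, because it depends on an unstated within-infant correlation and site effect.
3. The margin row is internally consistent but mislabelled. It overstates a simple 95% half-width 2.34-fold, ignoring site.

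None of this shows 600 to be too few. The phase 1a coverage gaps are 98.7 - 85.3 = 13.4 points for HR and 93.9 - 66.5 = 27.4 points for SpO2, several times any of the stated detectable differences. The section should be corrected, but no endpoint or analysis changes.

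**What to change.** Keep 600 and edit section 4 as follows.

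- Check the phase 1a source and correct either 3.46% or the SpO2 wireless coverage SD of 20.8.
- State the formula. Give both coverage figures as paired minimum detectable differences, 0.135 x SD of the within-infant wired-minus-wireless difference, with a provisional SD taken from the simultaneous phase 1a recordings. Say whether that SD is per infant or per recording.
- Either recompute the table row as 95% half-widths (0.0817 x SD), or keep the numbers and relabel the row as differences detectable with 90% power.
- Add one sentence saying that these figures treat infants as independent of site.

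The cost is a short recalculation and a few edited lines, with no extra infants. The drawback is that the paired SD comes from 25 pilot infants (96 recordings) monitored with an earlier sensor in another setting, and the text should say so.

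### The SpO2 coverage difference of 3.46% does not follow from the printed wireless SD of 20.8%; the parameters that reproduce the plan's other figures give 3.97%

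*Combined protocol and SAP*

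**What the plan says.** The sample-size paragraph of section 4 (Statistical Analysis and Rationale) sets 100 newborns at each of six sites, 600 in all. It gives the settings for its precision figures: "Assuming a two-sided significance of 0.05", "a study power of 0.9", and "accounting for the drop-out rate of 0.04 in all calculations".

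For HR coverage it reports phase 1a values of 98.7 ± 2.2% (wired) and 85.3 ± 14.3% (wireless), and states an effect size of 2.7%. For SpO2 coverage it reports 93.9 ± 6.3% (wired) and 66.5 ± 20.8% (wireless), and concludes that the study "can thus expect a difference of 3.46" percent. It then says that the table of agreement measures uses the same parameters. In that table, SpO2 VAF is 18.9 ± 20.8%, with an expected margin of error of 3.97%.

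**The concern.** Two SpO2 quantities carry the same printed SD, 20.8%, and are said to rest on the same alpha, power, drop-out and sample size. One is given 3.46% and the other 3.97%. The wording presents the coverage figure as a consequence of the SDs printed just before it, so a reader should be able to get from one to the other.

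The percentage of time with data displayed is the first feasibility outcome in section 2.2, and SpO2 had the lower phase 1a wireless coverage of the two signals reported. At stake is whether the 90% power attached to 3.46 points can be relied on, or whether a phase 1a result is misreported.

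**Working it through.** **Inputs, all from section 4.** Two-sided alpha 0.05 (z = 1.960); power 0.9 (z = 1.282); 600 infants less 4% drop-out, 600 × 0.96 = 576 evaluable. The ± values are read as standard deviations.

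**Formula.** The plan prints none. The one that fits its figures is the two-sample form with 576 per system: difference = (1.960 + 1.282) × SD × sqrt(2/576) = 0.191 × SD. For coverage, the SD that fits is the wireless one.

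**Reproducing the plan's figures:**

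| Quantity | Printed SD | 0.191 × SD | Stated |
|---|---|---|---|
| HR coverage (wireless) | 14.3 | 2.73 | 2.7 |
| HR VAF | 6.5 | 1.24 | 1.24 |
| SpO2 VAF | 20.8 | 3.97 | 3.97 |
| HR bias | 0.32 | 0.061 | 0.06 |
| SpO2 bias | 1.4 | 0.267 | 0.26 |
| HR correlation | 0.03 | 0.006 | 0.01 |
| SpO2 correlation | 0.23 | 0.044 | 0.04 |
| SpO2 proportionality constant | 0.01 | 0.002 | 0.00 |
| **SpO2 coverage (wireless)** | **20.8** | **3.97** | **3.46** |

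The HR proportionality constant has SD 0.00 and margin 0.00. The SpO2 bias margin is within rounding of its SD: 1.35 to 1.45 gives 0.258 to 0.277. Ignoring drop-out (n = 600) fits worse, giving 1.22 for HR VAF and 3.89 for SpO2 VAF.

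**SpO2 coverage is the exception.** Rounding does not explain it: SDs of 20.75 to 20.85 give 3.96 to 3.98. Working backwards, 3.46 / 0.191 = 18.1.

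**A check that needs no formula.** If both coverage figures are one multiplier times the wireless SD, the ratios must agree. For HR, 2.7/14.3 = 0.189 (2.65/14.3 = 0.185 to 2.75/14.3 = 0.192 allowing for rounding of 2.7). For SpO2, 3.46/20.8 = 0.166. They do not agree.

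**Other routes to 3.46:**

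- Power 0.80 gives 3.43 for SpO2 but 2.36 for HR.
- One-sided 0.05 gives 3.59 for SpO2.
- The root mean square of the wired and wireless SDs gives 2.94 for SpO2 and 1.95 for HR.
- The usual paired formula, (1.960 + 1.282) × SD of the difference / sqrt(576), cannot give 2.7 for HR. Even at a correlation of −1 the difference SD is 14.3 + 2.2 = 16.5, which gives 2.23.
- A paired-difference SD put into the 0.191 multiplier can give both figures, but only with a different correlation for each signal (see the objection).

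**Size if 20.8 is the intended input.** The standard error is 20.8 × sqrt(2/576) = 1.226. Then 3.46/1.226 − 1.960 = 0.863, which is a power of about 81%. The difference detectable at 90% power is 3.97 points, 0.51 above the stated figure.

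**The case against.** The strongest reply is that every printed number may be right. Both systems are worn by the same infant, so the natural SD for a coverage contrast is that of the within-recording difference, which section 4 does not print. With marginal SDs of 20.8 and 6.3, a difference SD of 18.1 needs a correlation of (20.8² + 6.3² − 18.1²) / (2 × 20.8 × 6.3), about 0.55. For HR, a stated 2.7 (2.65 to 2.75) implies a difference SD of 13.9 to 14.4, hence a correlation of about 0.03 to 0.27. All of these are possible values, and nothing requires the two signals to share one. The plan also applies the 0.191 multiplier to a paired quantity in its bias column. In addition, the formula is inferred, and its calibration on HR coverage rests on a figure given to one decimal.

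This stands as a possible explanation, so the choice is not simply between a wrong 3.46% and a wrong SD. It does not remove the point. The correlations are not in the documents, and 3.46% still does not follow from the SDs that the sentence offers as its basis.

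Three stronger inferences are tempting and not supported:

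- **The plan overstates what 600 infants deliver.** That holds only if the wireless SD of 20.8% was the intended input, which the documents do not settle.
- **The coverage SD was copied from the VAF entry.** The shared value is suggestive, but nothing shows it.
- **Equal SDs must always give equal figures.** This is true under the multiplier that fits the plan, not in general. VAF is one value per recording, whereas coverage is a contrast of two systems whose precision depends on both SDs and their correlation.

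**Conclusion.** The point holds as an unexplained inconsistency in one figure. Under the stated parameters and the multiplier that reproduces the plan's other figures, an SD of 20.8% gives 3.97%, not 3.46%; the stated figure corresponds to an SD of about 18.1. The documents do not show which number is at fault, or whether an unprinted SD was used.

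This rests on reading ± as SD, on 576 evaluable infants, and on the inferred formula, although the comparison of ratios does not need the formula.

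The practical effect is small. The phase 1a SpO2 coverage gap was 93.9 − 66.5 = 27.4 points, about seven times either figure. The sample size is set as 100 per site rather than derived from 3.46%, and section 4 names no test or success threshold for coverage. A reader might infer that the study is underpowered, since 90% power for 3.46 points with SD 20.8 would take 760 evaluable infants (792 before 4% drop-out). The documents do not support that, because nothing in them makes 3.46 points a target the study has to meet.

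**What to change.** Recheck the phase 1a SpO2 coverage data, then amend the sentence in section 4 according to what is found:

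- If the wireless SD of 20.8% is correct and was the intended input, restate 3.46% as 3.97%.
- If the printed SD is a misprint, replace it with the value computed from the phase 1a recordings. The 18.1 above is a diagnostic and should not be entered as the SD.
- If a paired-difference SD was used, print that SD and put HR coverage on the same basis.

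In each case, state the formula and the SD that enters it. The cost is one check of existing data and a correction of a sentence or two. The sample size does not change.

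### Correlation and variance accounted for serve as accuracy outcomes and feed subgroup comparisons, yet at fixed sensor error both move with each infant's signal spread, which the plan does not report

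*Combined protocol and SAP*

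**What the plan says.** Aim 3 (Section 2.2) concerns HR, RR, SpO2 and skin temperature "signals compared with the “standard of care” wired system. The following outcomes will be computed". Four outcomes follow: correlation coefficient, slope, "Variance accounted for" and bias.

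The analytical approach in Section 4 repeats these. It describes the correlation as "a statistical measure of the strength of a linear relationship between the two systems (correlation coefficient") and VAF as "the ratio of explained and target variance (variance accounted for"), and it adds "a Bland-Altman plot analysis to evaluate *bias* between the mean differences and estimate an agreement interval".

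Section 2.2 also states: "Further subgroup analyses will be conducted to assess for systematic differences in feasibility, safety, and accuracy of the wireless system". The comparisons are by country income level, sex, term versus preterm, delivery mode and skin pigmentation.

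The precision table in Section 4 covers the correlation C, the proportionality constant k, VAF and bias. It has no column for the agreement interval. Nowhere does the plan report the spread of each infant's signal, set an acceptable error, or rank the accuracy measures.

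**The concern.** Correlation and VAF measure association relative to signal variance. VAF, as Section 4 defines it, has the target signal's own variance as its denominator. Neither is an error in bpm, percentage points or degrees. A low value can mean a poor sensor or a calm infant, and a high value can mean a good sensor or a signal that swings widely.

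This matters most where accuracy is compared between groups. Two subgroups with the same sensor error but different signal spread would show different C and VAF, which could be reported as an accuracy difference. A real difference in error could equally be masked.

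The setting makes the issue live. Only clinically stable infants enrol (Section 3.3.2.2), and data collection ends if the infant needs intervention (Section 3.3.4). The phase 1a benchmarks come from 8-hour NICU recordings (Section 1.3), so their C and VAF need not carry over. That SpO2 will vary little in these infants is an expectation; the documents give no signal SD.

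**Working it through.** **Inputs from the documents.** Sample size 600; drop-out 0.04, two-sided 0.05 and power 0.9 (Section 4 text). Phase 1a averages from the Section 4 table: HR C 0.96 ± 0.03 and VAF 91.5 ± 6.5%; SpO2 C 0.53 ± 0.23, VAF 18.9 ± 20.8% and k 1.01 ± 0.01.

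**Assumed inputs.** The within-infant signal SD and the sensor error SD are not given, so ranges are shown. The 1.4% error SD below is an assumption. It is not the 1.4% in the table, which is the SD attached to the mean bias.

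**1. The plan's own margins.** With n = 600 × 0.96 = 576, the factor √2 × (1.960 + 1.282)/√576 = 0.1910 reproduces the table:
- SpO2 C: 0.23 × 0.1910 = 0.044 (stated 0.04)
- SpO2 VAF: 20.8 × 0.1910 = 3.97 points (stated 3.97)
- HR VAF: 6.5 × 0.1910 = 1.24 points (stated 1.24)

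This factor is a two-group detectable difference with 576 per group. For two halves of the sample (288 each) it grows by √2, so the SpO2 C margin becomes 0.044 × 1.414 = 0.062.

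**2. Error in both devices.** Let the infant's true signal have SD s, and let each device add independent error of SD e. Then
- C = s²/(s² + e²)
- VAF (one signal predicting the other with k = 1) = 1 − 2e²/(s² + e²) = 2C − 1
- RMS difference at zero bias = e√2

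With e = 1.4%, e² = 1.96:

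| s (SpO2, %) | C | VAF | RMS difference |
|---|---|---|---|
| 1 | 1/2.96 = 0.34 | −32% | 1.98% |
| 1.5 | 2.25/4.21 = 0.53 | 7% | 1.98% |
| 2 | 4/5.96 = 0.67 | 34% | 1.98% |
| 4 | 16/17.96 = 0.89 | 78% | 1.98% |
| 8 | 64/65.96 = 0.97 | 94% | 1.98% |

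Moving s from 1.5 to 2% shifts C by 0.14, more than three times the stated 0.04 and more than twice 0.062, with no change in error.

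**3. All error in the wireless device.** Now r = sx/√(sx² + se²) and VAF = 1 − se²/sx², where sx is the SD of the wired signal. With se = 1.5 points:
- sx = 1.5: r = 0.71, VAF = 0%
- sx = 3: r = 0.89, VAF = 75%

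The gaps are 0.19 in r and 75 points in VAF, while the limits of agreement are ±1.96 × 1.5 = ±2.94 points in both. A simulation of 300 infants per group gave mean r 0.70 and 0.89, with bias 0.00 and SD of differences 1.50 in each.

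**4. Using the document's HR figures.** VAF 91.5% gives se/sx = √(1 − 0.915) = 0.29 and r = 1/√1.085 = 0.96, matching the table. With that error held fixed:
- half the spread: se²/sx² = 0.085 × 4 = 0.34, so r = 1/√1.34 = 0.86 and VAF = 66%
- double the spread: se²/sx² = 0.085/4 = 0.021, so r = 0.99 and VAF = 98%

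**5. What C = 0.53 says about error.** From step 2, e/s = √(1/0.53 − 1) = 0.94. That fits e = 1.4% if s = 1.5%, and e = 4.7% if s = 5%. C alone cannot choose between them.

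**Limits.** Neither simple model fits the phase 1a SpO2 averages. Step 2 at C = 0.53 gives VAF 2 × 0.53 − 1 = 6%, and step 3 at VAF 18.9% gives r = 0.74. The figures show direction and scale; they do not predict this trial's results. Calculation per recording is inferred from the mean ± SD layout. Pooled values would also depend on spread between infants.

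**The case against.** **Agreement measures are already planned.** Section 4 includes Bland-Altman bias and an agreement interval, and Aim 3 lists bias. Under constant error variance these do not depend on signal spread. RMS difference follows from them as √(bias² + SD of differences²). This stands and reduces the harm. What remains is that the interval is absent from the Aim 3 list and the precision table, and no text makes it the basis for conclusions or subgroup comparisons.

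**Tracking measures have a use.** With s = 1 and e = 1.4, a wireless reading frozen at the infant's mean has RMS difference √(1 + 1.96) = 1.72%, lower than the working sensor's 1.98%. Correlation and VAF would expose that failure. This stands too, so they should be kept beside the error measures.

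**Stronger readings the documents do not support:**
- A reader might infer that the SpO2 VAF of 18.9% is impossible because C² is 0.53² = 28%. VAF equals C² only for a least-squares line with an intercept. The table's proportionality constant points to a fit without one. With k near 1, VAF = 2Cq − q², where q is the ratio of the two signals' SDs. C = 0.53 and q = 0.83 give 0.880 − 0.689, about 19%. What is missing is the formula.
- A reader might infer that sensor timing confounds delivery mode. Section 3.3.3 gives the same 10–20 minute window for the second system in both modes.
- A reader might take C and VAF as the primary accuracy result. The documents set no ranking and no pass mark.
- A reader might take C = 0.53 as proof of a narrow SpO2 range. Real sensor error could explain it as well.

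**Conclusion.** The point holds as a gap in how accuracy will be concluded and compared. Two of the four Aim 3 outcomes change with signal spread at constant sensor error, and the plan reports no spread and gives no rule for which measure decides. That C and VAF depend on spread follows from their definitions and needs no assumed value. The size does rest on assumptions: independent errors of constant SD and the illustrative SDs shown. Over those ranges C for SpO2 runs from 0.34 to 0.97 with RMS difference fixed at 1.98%, against a stated margin of 0.04. Whether the five subgroups actually differ in signal spread cannot be told from the documents, so false subgroup differences are a risk and not a prediction. The planned Bland-Altman analysis supplies most of what is needed once it is given its place.

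**What to change.** - Add the limits of agreement and the RMS difference (wireless minus wired) to the Aim 3 outcomes for HR, RR, SpO2 and skin temperature, and add the limits to the precision table.
- State in Section 4 that overall and subgroup accuracy conclusions rest on bias and the spread of the differences.
- Keep C and VAF as secondary measures of how well the sensor tracks change. Print them beside the within-infant SD of the wired signal. Do not read them alone as sensor error or as a subgroup difference in accuracy.
- State the VAF formula (which signal is the target, and whether the fit has an intercept) and whether C and VAF are computed per recording or pooled.

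The cost is wording and a small amount of extra analysis on data already logged by BioDASH. Enrolment, procedures and sample size are unaffected. C and VAF become secondary.
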